9.2.9 Other Safety Considerations

Any significant worsening noted during interim or final physical examinations, ECG, x-ray filming, or any other potential safety assessment required or not required by protocol should also be recorded as a nonserious AE or serious AE, as appropriate, and reported accordingly.

9.3 Overdose

An overdose is defined as the accidental or intentional administration of any dose of a product that is considered both excessive and medically important. All occurrences of overdose must be reported as an SAE (see Section 9.2.1).

9.4 Safety Assessment

Planned time points for all safety assessments are listed in the Schedule of Activities.

AEs will be assessed continuously during the study and for 100 days after the last dose of nivolumab. AEs will be evaluated according to the NCI CTCAE v5.0 and should be followed per requirements in Section 9.2.1 and [Section 9.2.2](#). AEs will be coded using the most current version of Medical Dictionary for Regulatory Activities (MedDRA) and reviewed for potential significance and importance. Participants should be followed until all treatment-related AEs have recovered to baseline or are deemed irreversible by the investigator.

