LFT Assessments	X ^a		X	X	Collect predose. Includes AST, ALT, total bilirubin, direct bilirubin (only if total bilirubin is elevated), alkaline phosphatase, and GGT (only when alkaline phosphatase is increased to \geq Grade 2).
Pregnancy Test (WOCBP)	X				Serum or urine pregnancy test must be performed (urine pregnancy test: minimum sensitivity 25 IU/L or equivalent units of hCG) within 24 hours prior to administration of study drug. If pregnancy test is positive, hold all study drugs and perform confirmatory testing. If pregnancy is confirmed, permanently discontinue all study drugs and immediately notify sponsor per Section 9.2.5 .
Concomitant Medication Assessments		X			Review prior to dosing.
Monitor for Nonserious Adverse Events		X			Nonserious AEs will be collected starting with the first dose of study drug and through 100 days after completion of study drugs (or 30 days if subject only received BMS-986205).
Monitor for Serious Adverse Events		X			All SAEs must be collected from the date of participant's written consent until 100 days post last dose of study drugs (or 30 days if participant only received BMS-986205) or participant's participation in the study if the last scheduled visit occurs at a later time. SAEs reported in the BMS EDC tool should be approved within 5 business days of entry.
Pharmacokinetic (PK) Assessments		X			See Section 9.5.1 and Table 9.5.2-1 . Performed in all subjects.
Urine for p-Chloroaniline	X	X			See Section 9.5.1 . Urine (0 to 24 hours) collection start after first dose. An approximately 50 mL aliquot of each urine collection (0 to 8 hours, 8 to 24 hours) will be frozen for shipment.

Table 2-2: On-Treatment: BMS-986205 Monotherapy (One 14-Day Cycle) Procedure Outline (CA017076)

Procedure	Cycle 0 D1	Cycle 0 D2	Cycle 0 D8	Cycle 0 D14	Notes
Study Drug Administration					
Dispense BMS-986205	X				BMS-986205 should be dispensed to participants at Day 1 of Cycle 0.
BMS-986205 Administration		Daily			BMS-986205 administration must be performed daily. BMS-986205 must be administered with a meal at approximately the same time each day. Dosing and associated meal should occur at the site on days when serial PK is collected.
Pill Diary		Daily			Pill diary should be provided to participants at Day 1 of Cycle 0. Pill diary must be completed with each administered daily dose of BMS-986205. Review pill diary during each visit for compliance of daily administration of BMS-986205. Collect pill diary at the completion of each cycle.

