Chemistry (Excluding LFTs)	X	X	X	X	X	X		X	Predose; includes assessments for sodium, potassium, chloride, total serum calcium, magnesium, phosphorus, BUN, creatinine, c-reactive protein, glucose, total protein, albumin, amylase, lipase, and LDH.
Methemoglobin	X	X	X	X	X			X	Collect predose. Starting with C2D1, collect every cycle and as clinically indicated.. Methemoglobin levels to be assessed on arterial or venous blood sample.
Reticulocyte counts, haptoglobin and LDH	X	X	X	X	X			X	Reflex when methemoglobin is elevated over ULN. Additional samples as clinically indicated.
CBC with Differential and Platelets	X	X	X	X	X	X		X	Predose.

Table 2-3: On-Treatment: BMS-986205 + Nivolumab (Multiple 4-Week Cycles) Procedure Outline (CA017076)

Procedure	Cycle 1 (4 weeks)				Cycle 2-12 (4-week cycles)			End of Treatment ^{a,b,c}	Notes
	D1	D8	D15 (±2 days)	D22 (±2 days)	D1	D15 (±2 days)	D22-28		
LFT Assessments	X	X	X	X	X	X		X	Predose; includes AST, ALT, total bilirubin, direct bilirubin (only if total bilirubin is elevated), alkaline phosphatase, and GGT (only when alkaline phosphatase is increased to ≥ Grade 2).
Thyroid Function Tests					X See notes (every 2 cycles)			X	Collect every 2 cycles, predose, beginning with C3D1 and at the end of treatment. To include TSH with reflex testing to free T3 and free T4 if TSH abnormal. Results should be examined by the investigator or appropriate designee within 48 hours of dose administration.
Pregnancy Test (WOCBP)	X				X			X	Serum or urine pregnancy test must be performed (urine pregnancy test: minimum sensitivity 25 IU/L or equivalent units of hCG) within 24 hours prior to administration of nivolumab. If pregnancy test is positive, hold all study drugs and perform confirmatory testing. If pregnancy is confirmed, permanently discontinue all study drug and immediately notify sponsor per Section 9.2.5 .

Table 2-3: On-Treatment: BMS-986205 + Nivolumab (Multiple 4-Week Cycles) Procedure Outline (CA017076)

Procedure	Cycle 1 (4 weeks)				Cycle 2-12 (4-week cycles)			End of Treatment ^{a,b,c}	Notes
	D1	D8	D15 (±2 days)	D22 (±2 days)	D1	D15 (±2 days)	D22-28		
Adverse Event Reporting and Concomitant Medication Assessments									
Concomitant Medication Assessments	X	X	X	X	X	X	X	X	Review prior to dosing.
Monitor for Nonserious Adverse Events				X					Nonserious AEs will be collected starting with the first dose of study drug and through 100 days post last dose of study drugs.

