Monitor for Serious Adverse Events				X					All SAEs must be collected from the date of subject's written consent until 100 days postdiscontinuation of nivolumab or subject's participation in the study if the last scheduled visit occurs at a later time. SAEs reported in BMS EDC should be approved within 5 business days of entry.
Sample Collection									
PK/ADA Assessments				X					Performed in all subjects. See Section 9.5.2 .
Pharmacodynamic Assessments				X					Performed in all subjects. See Section 9.6 .

Table 2-3: On-Treatment: BMS-986205 + Nivolumab (Multiple 4-Week Cycles) Procedure Outline (CA017076)

Procedure	Cycle 1 (4 weeks)				Cycle 2-12 (4-week cycles)			End of Treatment ^{a,b,c}	Notes
	D1	D8	D15 (±2 days)	D22 (±2 days)	D1	D15 (±2 days)	D22-28		
Efficacy Assessments									
Diagnostic Imaging						X		X	To be collected at the end of Cycle 2 and then every 8 weeks (± 1 week), by methods used at baseline. See Section 9.1 and Section 9.4.2 . Same modality/scanner should be used for all assessments. Assessed by RECIST v1.1; see Appendix 5 . Assessment must be performed prior to initiating the next cycle of treatment.
Brain Imaging					X				As clinically indicated; see Section 9.1 and Section 9.4.2 .
Bone Scan Imaging					X				As clinically indicated; see Section 9.1 and Section 9.4.2 .
Study Drug Administration									
Dispense BMS-986205	X				X				BMS-986205 should be dispensed to participants at Day 1 of each cycle.
BMS-986205 Administration	X				Daily				BMS-986205 administration must be performed daily. BMS-986205 must be administered with a meal at approximately the same time each day. Dosing and associated meal should occur at the site on days when serial PK is collected.
Nivolumab Administration	X				X				Nivolumab should be administered at Day 1 of each cycle.

Table 2-3: On-Treatment: BMS-986205 + Nivolumab (Multiple 4-Week Cycles) Procedure Outline (CA017076)

Procedure	Cycle 1 (4 weeks)				Cycle 2-12 (4-week cycles)			End of Treatment ^{a,b,c}	Notes
	D1	D8	D15 (±2 days)	D22 (±2 days)	D1	D15 (±2 days)	D22-28		
Pill Diary	X			Daily				X	Pill diary should be provided to participants at Day 1 of each cycle. Pill diary must be completed with each administered daily dose of BMS-986205. Review pill diary during each visit for compliance of daily administration of BMS-986205. Collect pill diary at the completion of each cycle and EOT.

^a EOT is defined as the visit where decision is made to discontinue the subject from treatment.

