^b For subjects who complete all scheduled cycles of therapy, the EOT visit will be the same as the last scheduled and completed on-treatment visit (eg, Cycle 2 Day 22) and the start of the Week 1 Clinical/Safety Follow-Up visit.

^c For subjects who do not complete all scheduled cycles of therapy, the EOT visit will be the most recent on-treatment visit (with all available safety and response data) and does not need to be repeated, and will be considered the start of the Week 1 Clinical/Safety Follow-Up visit.

Table 2-4: Follow-Up Procedure Outline (CA017076)

Procedure	Clinical Safety Follow-Up ^a			Notes
	FU 1 30 days (± 10 days)	FU 2 60 days (± 10 days)	FU 3 100 days (± 10 days)	
Safety Assessments				
Symptom-Directed Physical Examination	X	X	X	
Vital Signs	X	X	X	Includes body temperature, seated blood pressure, and heart rate. Blood pressure and heart rate should be measured after the participant has been seated quietly for at least 5 minutes.
Laboratory Tests				
Chemistry (Excluding LFTs)	X	X	X	Includes assessments for sodium, potassium, chloride, total serum calcium, magnesium, bicarbonate/carbon dioxide, phosphorus, BUN, creatinine, glucose, total protein, albumin, amylase, lipase, and LDH.
Methemoglobin	X	X	X	Only to be drawn if above ULN at last assessment; not required during follow up.
Reticulocyte count, LDH, and haptoglobin	X	X	X	Reflex when methemoglobin is elevated over ULN. Additional samples as clinically indicated.
CBC with Differential and Platelets	X	X	X	Additional samples as clinically indicated.
LFT Assessment	X	X	X	For participants with LFT abnormalities following the last dose of study drug, consider collecting weekly until normalized. Includes AST, ALT, total bilirubin, direct bilirubin (only if total bilirubin is elevated), alkaline phosphatase, and GGT (only when alkaline phosphatase is increased to ≥ Grade 2).

Table 2-4: Follow-Up Procedure Outline (CA017076)

[figure not shown]
Procedure	Clinical Safety Follow-Up ^a			Notes
	FU 1 30 days (± 10 days)	FU 2 60 days (± 10 days)	FU 3 100 days (± 10 days)	
Thyroid Function Tests	X	X	X	To include TSH with reflex testing (free T3 and free T4).
Pregnancy Test	X	X	X	For WOCBP; serum or urine pregnancy test may be performed (clinic urine pregnancy test: minimum sensitivity 25 IU/L or equivalent units of hCG). If positive, perform confirmatory testing. If pregnancy is confirmed, immediately notify sponsor per Section 9.2.5 .

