Investigators are not obligated to actively seek AEs or SAEs in former study participants. However, if the investigator learns of any SAE, including a death, at any time after a participant has been discharged from the study, and he/she considers the event reasonably related to the study treatment or study participation, the investigator must promptly notify the sponsor.

The method of evaluating, and assessing causality of AEs and SAEs and the procedures for completing and reporting/transmitting SAE reports are provided in [Appendix 3](#).

9.2.2 *Method of Detecting AEs and SAEs*

Adverse events can be spontaneously reported or elicited during open-ended questioning, examination, or evaluation of a participant. Care should be taken not to introduce bias when collecting AE and/or SAEs. Inquiry about specific AEs should be guided by clinical judgement in the context of known AEs, when appropriate for the program or protocol.

9.2.3 *Follow-up of AEs and SAEs*

- Nonserious AEs should be followed to resolution or stabilization, or reported as SAEs if they become serious (see [Appendix 3](#)).
- Follow-up is also required for nonserious AEs that cause interruption or discontinuation of study treatment and for those present at the end of study treatment as appropriate.
- All identified nonserious AEs must be recorded and described on the nonserious AE page of the CRF (paper or electronic). Completion of supplemental CRFs may be requested for AEs and/or laboratory abnormalities that are reported/identified during the course of the study.

[figure not shown]
All SAEs will be followed until resolution, until the condition stabilizes, until the event is otherwise explained, or until the participant is lost to follow-up (as defined in [Section 8.3](#)).

Further information on follow-up procedures is given in [Appendix 3](#).

9.2.4 *Regulatory Reporting Requirements for SAEs*

- Prompt notification by the investigator to the sponsor of SAEs is essential so that legal obligations and ethical responsibilities towards the safety of participants and the safety of a product under clinical investigation are met.
- An investigator who receives an investigator safety report describing SAEs or other specific safety information (eg, summary or listing of SAEs) from the Sponsor will file it along with the Investigator's Brochure and will notify the IRB/IEC, if appropriate according to local requirements.

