## **6 STUDY PERIODS, TREATMENT REGIMENS AND POPULATIONS FOR ANALYSES**

### **6.1 Study Periods**

- Baseline period:
  - Baseline evaluations or pre-treatment events will be defined as evaluations or events that occur before the date and time of the first dose of study treatment. Evaluations (laboratory tests, pulse oximetry, vital signs) on the same date and time of the first dose of study treatment will be considered as baseline evaluations. Events (AEs) on the same date and time of the first dose of study treatment will not be considered as pre-treatment events.
  - In cases where the time (onset time of event or evaluation time and dosing time) is missing or not collected, the following definitions will apply:
    - ◆ Pre-treatment AEs will be defined as AEs with an onset date prior to but not including the day of the first dose of study treatment;
    - ◆ Baseline evaluations (laboratory tests, pulse oximetry, vital signs) will be defined as evaluations with a date (and time if collected) on or prior to the date of first dose of study treatment.
  - If there are multiple valid observations in the baseline period, then the latest non missing observation will be used as the baseline in the analyses. If multiple observations exist on the latest collection date (and time if collected), the record with the latest data entry date and time will be used. If multiple observations exist on the latest collection date (and time if collected) and data entry date and time, then the first observation is used as baseline, unless otherwise specified.
- For nivolumab Anti-Drug Antibody (ADA), the baseline record of IDO1 inhibitor immunogenicity (IMG) evaluation must be less than the date and time of the first Nivolumab/IDO1 inhibitor dose date and time.
- Post baseline period:
  - On-treatment AEs will be defined as AEs with an onset date and time on or after the date and time of the first dose of study treatment (or with an onset date on or after the day of first dose of study treatment if time is not collected or is missing). For subjects who are off study treatment, AEs will be included if event occurred within a safety window of 100 days after the last dose of study treatment if a participant received BMS-986205 + NIVO (or 30 days after the last dose of study treatment if a participant received only BMS-986205). No “subtracting rule” will be applied when an AE occurs both pre-treatment and post-treatment with the same preferred term and grade.

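### The protocol gives two starting points for the 100-day adverse event window, and no contact is scheduled on the day the window closes

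*Protocol*

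**What the plan says.** The stopping rules for AE collection fall into two groups.

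- **Counted from nivolumab.** Protocol Section 9.4: "AEs will be assessed continuously during the study and for 100 days after the last dose of nivolumab". It gives no alternative for someone who received only BMS-986205. The serious-AE row of Table 2-3 runs until "100 days postdiscontinuation of nivolumab", or to the last scheduled visit if that is later. The serious-AE row of Table 2-1 uses the same anchor, with a 30-day alternative for BMS-986205 only.
- **Counted from the last dose of study drug, or end of dosing.** The nonserious-AE row of Table 2-3: "Nonserious AEs will be collected starting with the first dose of study drug and through 100 days post last dose of study drugs". The nonserious-AE row of Table 2-2: "through 100 days after completion of study drugs (or 30 days if subject only received BMS-986205"; its serious-AE row and both AE rows of Table 2-4 use the last dose of study drugs, with the same 30-day alternative. Section 9.2.1 counts serious AEs from the end of dosing. SAP Section 6.1 counts AEs "within a safety window of 100 days after the last dose of study treatment" for combination participants, and 30 days for those who received only BMS-986205.

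On visits, Table 2-4 lists the closing visit as "FU 3 100 days (± 10 days", with the days counted from the last dose of study drugs (footnote a). Participants who received only BMS-986205 have a single visit at Day 30, with the same tolerance. Section 5.1 requires follow-up for a minimum of 100 days, or 30 days for BMS-986205 only. Section 8.1.1 requires 100 days with no 30-day alternative.

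**The concern.** AE and serious-AE incidence is part of the primary endpoint (Protocol Table 4-1). The SAP counts every AE in a fixed window after the last dose, so an event that nobody asked about is counted as no event. Two features of the plan put that at risk. A site that reads Section 9.4 alone would close AE collection on a different day from a site that reads Table 2-4. And a site may hold the last visit before the window closes, with nothing scheduled afterwards.

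With 12 participants, one missed event moves an incidence by 1/12, or 8.3 percentage points. Sections 1 and 7.4 say the safety profile will be compared with that of non-Chinese patients on the same regimen, so uneven ascertainment would carry into that comparison.

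**Working it through.** **The plan's own figure.** Protocol Section 5.2 and SAP Section 5 state a 90% probability that 12 participants show at least one case of an AE with 18% incidence. 1 − (1 − 0.18)^12 = 1 − 0.82^12 = 0.908. The figure reproduces. It presumes that events in the window are ascertained.

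**Distance between the anchors.** Nivolumab is given on Day 1 and BMS-986205 daily in a 28-day cycle (Section 5.1). After a full last cycle the last doses are 28 − 1 = 27 days apart. One hundred days after nivolumab is then Day 100 − 27 = 73 after the last BMS-986205 dose, so the two stated end dates differ by 27 days. With last doses 7 or 14 days apart, the difference is 7 or 14 days.

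**Whether those 27 days would go unobserved.** Follow-up visits are counted from the last dose of study drugs. The earliest permitted closing visit is Day 90 on that clock, which is Day 90 + 27 = 117 after nivolumab. AE monitoring is marked at that visit in Table 2-4. A scheduled AE contact therefore still takes place after Day 73. For serious AEs, the clause extending collection to a later last visit closes 90 − 73 = 17 of the 27 days even if the visit is as early as allowed, and all 27 if it is on or after Day 100.

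**Visit tolerance.**

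- Combination: 100 − 10 = Day 90, leaving 10/100 = 10% of the SAP window with no later scheduled contact.
- BMS-986205 only: 30 − 10 = Day 20, leaving 10/30 = 33%.

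**Illustration of the effect on the 90% figure.** Assume that AEs are spread evenly over the time at risk, that all 12 participants lose the same number of days, and that nothing is recovered later. The observable incidence is then 0.18 × (1 − days lost / days at risk).

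| Time at risk | Days lost | Observable incidence | Probability of at least 1 in 12 |
|---|---|---|---|
| 50 weeks + 100 days = 450 days | 10 | 0.176 | 90.2% |
| 14 + 28 + 100 = 142 days | 10 | 0.167 | 88.9% |
| 14 + 30 = 44 days (BMS-986205 only) | 10 | 0.139 | 83.4% |

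The last row is an extreme, because it makes all 12 participants lead-in-only, while Section 5.2 replaces anyone who stops before or at Cycle 1 Day 1.

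**The case against.** The strongest reply is that an early visit does not end collection. Section 5.1 sets a minimum of 100 (or 30) days of follow-up, and the tables require nonserious AEs to be collected "through 100 days post last dose of study drugs". A visit on Day 90 is within its window, but stopping collection that day would break these rules. This stands. A reader might infer that the windows are certain not to be fully observed; the documents support only that they may not be. What remains is an obligation with no scheduled contact to meet it, and a tolerance that contradicts a stated minimum.

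A reader might also take "Investigators are not obligated to actively seek AEs or SAEs in former study participants" in Section 9.2.1 as releasing sites from Day 90 onward. The next sentence of that section concerns participants already discharged from the study, and someone still inside a required follow-up period has not been discharged. The same section also requires any later serious AE thought to be related to be reported.

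A third tempting reading is that 27% of the SAP window would be lost, or that the 27 days and the 10 days add up. Visits run on the study-drug clock, and the later-visit clause covers most or all of the gap for serious AEs. Nonserious AEs have no such clause, but the nonserious rows of all three treatment and follow-up tables already use the study-drug anchor. Only Section 9.4 departs from it.

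**Conclusion.** The point holds as two separate defects. First, the protocol's stopping rules for AE and serious-AE collection disagree, by 27 days after a full last cycle, and Section 9.4 leaves participants who never received nivolumab without a rule. This is a contradiction in the text that sites could resolve differently; it is not an estimate of lost data. Second, the 10-day tolerance on the last visit conflicts with the minimum follow-up, and no contact is scheduled at window close. Up to 10 of 100 days, or 10 of 30 days for lead-in-only participants, may be incompletely observed.

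The practical effect is modest. If every participant lost 10 days, the 90.8% detection probability would fall to 90.2% after a full course and 88.9% after one combination cycle, on the assumption of evenly spread events. For lead-in-only participants the risk comes only from the visit tolerance, since no stated rule gives them a window shorter than 30 days. It is worth correcting because it concerns a primary endpoint and costs little.

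**What to change.** - Use one anchor, the last dose of either study drug (30 days if only BMS-986205 was received), in Section 9.4 and in the serious-AE rows of Tables 2-1 and 2-3, to match SAP Section 6.1. Reconcile Section 8.1.1 in the same edit.
- Keep the 10-day tolerance on visits. When the last visit is held before Day 100 (or Day 30), close AE and serious-AE collection by a telephone contact on or after that day.
- A one-sided window for the last visit (Day 100 or Day 30, plus 10 days) would also work for AEs, but SAP Section 6.1 admits laboratory, oximetry and vital-sign evaluations only up to 100 (or 30) days after the last dose. Results from Days 101 to 110, or 31 to 40, would drop out, and laboratory abnormalities are part of the primary endpoint. If that option is chosen, the SAP evaluation window must be extended to include that visit.

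The cost is a wording change in Sections 8.1.1 and 9.4 and two tables, a line adding the closing contact, and one brief telephone call for each participant whose last visit was early. No clinic visit is added.
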